## **9 STUDY OBJECTIVES**

To assess the efficacy and tolerability of Vicinium when administered as a monotherapy intravesical instillation in subjects with non muscle-invasive bladder cancer - CIS, high-grade Ta or any grade T1 papillary disease or CIS plus papillary disease who failed previous treatment (i.e., not those who are intolerant) with BCG.

### **9.1 Primary Endpoint**

Complete response rate in subjects with CIS (with or without resected papillary disease) whose disease is refractory or relapsed in 6 months or less following adequate BCG treatment (see **Section 17.5**).

Duration of response (DoR) will be estimated (Kaplan-Meier Estimate) for those subjects with CIS (with or without resected papillary disease) who experience a complete response.

## 9.2 Secondary Endpoints

- Complete response rate and DoR in subjects with CIS (with or without papillary disease) whose disease is refractory or relapsed from 6 months to 11 months following adequate BCG treatment
- Complete response rate and DoR in all subjects with CIS (with or without papillary disease) following adequate BCG treatment
- Event-free survival (EFS) in all subjects.
- Complete response rate in subjects after 3, 6, 9, 12, 15, 18, 21, and 24 months in subjects with CIS.
- Time to cystectomy in all subjects.
- Time to disease recurrence in all subjects.
- Progression-free survival (PFS) in all subjects.
- Overall survival (OS) in all subjects.
- Safety and tolerability of Vicinium therapy in all subjects.

## 9.3 Exploratory Endpoints

To evaluate biomarkers that may be associated with response or disease progression or treatment failure which may include for example, EpCAM status, tumor subtype morphology, furin levels in tumor cell endosomes, presence of a glycosaminoglycan coat and presence of receptors that could impede a host anti-tumor immune response such as PD-L1.

# 10 STUDY DESIGN

This is an open-label, non-randomized, multicenter, multiple-dose, study of Vicinium in approximately 134 subjects with histologically-confirmed non muscle-invasive carcinoma in situ (CIS) and/or papillary disease (high grade Ta or any grade T1) of the bladder who failed previous treatment (i.e., not those who are intolerant) with BCG.

All subjects must have received “adequate BCG treatment” defined as at least 2 courses of full dose BCG i.e., at least one induction course of at least 5 doses given within 7 weeks, and a second course (maintenance or second induction) of at least 2 doses given within 6 weeks. Full dose BCG is

- TICE® BCG: one vial of TICE containing 1 to 8 x 10^8 colony-forming units (CFU) equivalent to approximately 50 mg (wet weight)
- ImmuCyst® BCG: one vial of ImmuCyst containing 81 mg (dry weight) equivalent to approximately 10.5 ± 8.7 x 10^8 CFU

or equivalent.

The “5+2” doses must be given within approximately 1 year (i.e., start of one course to the start of a second course within 12 months ±1 month) and given to treat the same disease episode with which the subject is enrolling. Additional doses and courses of BCG are permitted as part of “adequate

BCG.” All subjects must have disease for which the investigator would not treat with additional BCG at this time.

Three cohorts of subjects will enroll:

- Cohort 1: Subjects with CIS with or without associated papillary disease whose disease is determined to be refractory or relapsed within 6 months of the last dose of adequate BCG treatment.
- Cohort 2: Subjects with CIS with or without associated papillary disease whose disease is determined to be refractory or relapsed more than 6 months but within 11 months of the last dose of adequate BCG treatment.
- Cohort 3: Subjects with high-grade Ta or any grade T1 papillary disease (without CIS) whose disease is determined to be refractory or relapsed within 6 months of the last dose of adequate BCG treatment.

For eligibility and cohort assignment 6 months is defined as 30 weeks i.e., 26 weeks (6 months) plus an additional 4 weeks to accommodate scheduling variations and for diagnostic work-up and 11 months is defined as 50 weeks i.e., 48 weeks (11 months) plus an additional 2 weeks to accommodate scheduling variations and for diagnostic work-up.

Of the 134 subjects,  $\geq 77$  will accrue to Cohort 1. Up to 57 additional subjects in total may accrue to Cohorts 2 and 3. This is an outpatient study. All treatments may be administered in the study clinic.

All diagnostic pathology (bladder tissue and urine cytologies and if performed, tissue from prostatic urethral biopsies) will be reviewed and graded by an independent pathologist and cytopathologist with experience in NMIBC diagnoses. The details of sample handling and logistics will be provided in a separate laboratory manual.

The sample used for determining subject eligibility for inclusion into the trial (post-BCG biopsy) must be reviewed and signed off by the pathologist prior to study enrollment and start of study treatment. All other samples will be read in a timely fashion and the results will be available to study investigators via the electronic CRF.

[figure not shown]
Time points for this study will use a week–day convention. For each subject, Day 1 is defined as the date that the subject first receives study drug and will be designated as Week 1 Day 1 (W1D1). The day before this date is Day  $-1$  (W $-1$ D $-1$ ; there is no Day 0).

Each subject's study course consists of a Screening Period, a 12-week Induction Phase, a Maintenance Phase and a Post-Treatment Evaluation. Subjects will receive intravesical Vicinium instillations twice weekly (BIW) for 6 weeks followed by once weekly for 6 weeks for a total of 18 doses in the Induction Phase. The twice-weekly doses are to be administered at least 48 hours apart (and no more than 2 doses may be administered within a calendar week, i.e., within a Sunday through Saturday). During the Maintenance Phase, Vicinium is administered once every other week. Total duration of treatment (combined Induction and Maintenance Phases) is up to 2 years (104 weeks). Subjects with a protocol-defined treatment failure (see [Section 14.2](#)) or other criteria for study drug discontinuation (see [Section 11.3](#)) will be withdrawn from the study.

[figure not shown]
Subjects will be evaluated for disease every 13 weeks ([Figure 1](#), [Section 10.4](#), [Section 10.5](#)). The first on-study evaluation will occur after the Induction Phase. At Week 12, a urine sample for cytology will be collected. In Week 13, subjects will undergo cystoscopy. Subjects without

treatment failure (see **Section 14.2**) or other criteria necessitating treatment discontinuation (**Section 11.3**) will enter the Maintenance Phase.

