### **11.3 Study Withdrawal Criteria**

Subjects are free to withdraw from treatment or from any further participation in the study (i.e., withdraw consent) at any time and without prejudice to further treatment. The Investigator should discuss with the subject if they want to withdraw from further treatment only (i.e., additional data will be collected) or from all further study participation at which time no data will be collected for the subject. The investigator must withdraw a subject from all further study participation if that subject withdraws consent. No additional evaluations will be done or data collected for subjects who withdraw consent. All subjects withdrawing from further study treatment should have Post-Treatment evaluation 30 – 37 days after the last dose of study treatment and receive follow up disease evaluation (every 3 months ([Section 10.6](#)) and until a protocol-defined event as well as be contacted for data secondary endpoint (PFS, OS). The reasons and details relevant to subject withdrawal must be recorded in the case report form (CRF). The Investigator must notify the Medical Monitor if a subject is withdrawn from the study.

Subjects must be withdrawn from study drug for any of the following reasons:

- Withdrawal of informed consent
- Pregnancy ([Section 12.5](#))
- Treatment failure ([Section 14.2](#))
- Documented extravesical (i.e., upper or lower tract) urothelial carcinoma
- Development of a second malignancy that requires systemic therapy
- Cystectomy
- Unacceptable toxicity
- Persistent non-compliance with the protocol requirements
- Treating physician / study Investigator concludes that it would be in the subject's best interest
- Intercurrent illness that, in the judgment of the Investigator, may affect assessments of clinical status to a significant degree, and that requires discontinuation of study drug.
- Sponsor terminates the study.

Subjects may be considered withdrawn if they fail to return for visits, or become lost to follow-up for any other reason. Every attempt should be made to re-establish contact for subjects who are lost to follow-up (i.e., those subjects whose status is unclear because they fail to appear for study visits without stating an intention to withdraw). The Investigator should undertake appropriate due diligence and document steps taken to contact the subject (e.g., dates of telephone calls, registered letters).

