Subjects' disease status will be evaluated based on cystoscopy (and biopsies if indicated) and urine cytology at the end the Induction Phase (week 13) and every 13 weeks during the Maintenance Phase (i.e., Week 26, Week 39, Week 52, Week 65, Week 78, Week 91, Week 104) regardless of dosing interruptions or delays. For subjects who discontinue treatment for reasons other than disease progression ([Section 14.2](#)), cystectomy or death, the every 13-week disease evaluation should continue for the determination of secondary endpoints e.g., event-free survival, progression-free survival. Every effort should be made to stay on this evaluation schedule, however, a window of one week before and up to 2 weeks after these time points is permitted (e.g., the Week 26 cystoscopy and urine for cytology may be performed from week 25 to week 28, but as close to Week 26 as possible). The complete evaluation to determine disease status may require a repeat cytology and repeat cystoscopy with biopsies (See [Table 7](#)) and should be completed as soon as possible following the every 13-week timepoint. On cystoscopy, any areas suspicious for disease must be biopsied. In situations where there are no suspicious lesions on cystoscopy but a positive or suspicious result on urine cytology, random bladder biopsies will be obtained from the locations of disease identified at Screening (i.e., by screening biopsies and the screening bladder mapping) and from other areas of the bladder so that all the following areas of the bladder have been biopsied: the dome, the posterior wall, the left and right lateral walls, the trigone and the bladder neck, and in males, the prostatic urethra. A second urine cytology will also be required at the time of evaluation if the result of the first urine cytology is suspicious for urothelial carcinoma. The use of other diagnostic evaluations (e.g. urine FISH) or the performance of additional urine cytology, cystoscopies, and/or biopsies not mandated by the protocol may be performed when clinically indicated per the investigator's clinical judgment or standard of care. Results of urine FISH will not be considered in the response evaluation but may be used by the investigator to guide additional (non-protocol mandated) evaluations.

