EFS is defined as the interval from the date of first dose of study treatment to an event. Subjects who have a treatment failure or die following the post induction visit will be treated as having an event on the date of treatment failure or death. Subjects without evidence of a treatment failure who are diagnosed with upper or lower urinary tract urothelial carcinoma by histology, cytology or radiographic evidence will be censored at the date of diagnosis. Subjects without evidence of a treatment failure who undergo cystectomy will be censored at the date of cystectomy. All other subjects will be censored at the time of last assessment including long-term follow up.

Censoring rules for the analysis of EFS are presented in the table below.

Table: Censoring scheme for EFS

Situation	Date of Event or Censoring	Outcome
Treatment failure	Date of treatment failure	Event
Death without treatment failure and occurring prior to treatment discontinuation	Date of death	Event
Death without treatment failure and occurring after treatment discontinuation	Date of last evaluable disease assessment on or prior to treatment discontinuation ^a	Censored ^a
No baseline disease assessment	Date of first dose	Censored
No on-study disease assessments and no death	Date of first dose	Censored
No treatment failure and no death	Date of last evaluable disease assessment	Censored
New anti-cancer therapy received without treatment failure and reported prior to or on the same day as disease assessment	Date of last evaluable disease assessment on or prior to the date of initiation of subsequent therapy	Censored
Second non-NMIBC cancer reported prior to or on the same day as disease assessment	Date of last evaluable disease assessment on or prior to the date of diagnosis of non-NMIBC cancer	Censored
a This censoring rule acknowledges that disease assessments were not recorded after treatment discontinuation due to an AE.		

Cystectomy-Free Days

Cystectomy-free days is defined as the time from the date of first dose of study treatment to physical removal of the bladder. Subjects who are alive and do not have their bladder removed will be censored at the time of last contact.

Censoring rules for the analysis of cystectomy-free days are presented in the table below.

Table: Censoring scheme for Cystectomy

Situation	Date of Event or Censoring	Outcome
Cystectomy	Date of cystectomy	Event
Death without cystectomy	Date of death	Censored
No cystectomy	Date of last contact	Censored

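### Protocol Section 10 takes subjects who stop drug out of the study, while Sections 10.6, 11.3 and 14 keep them in follow-up; the passages need to be reconciled

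*Protocol*

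**What the plan says.** Protocol Section 10 (Study Design) states that subjects with a protocol-defined treatment failure, or with other criteria for stopping study drug under Section 11.3, "will be withdrawn from the study".

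Section 11.3 introduces the same criteria differently: "Subjects must be withdrawn from study drug for any of the following reasons". It then requires that "All subjects withdrawing from further study treatment should have Post-Treatment evaluation 30 – 37 days after the last dose of study treatment", followed by disease evaluation until a protocol-defined event and contact for PFS and OS. It closes data collection for one group only: "No additional evaluations will be done or data collected for subjects who withdraw consent".

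Other protocol text agrees with Section 11.3. Section 14 says that, for subjects who stop treatment for reasons other than progression, cystectomy or death, "the every 13-week disease evaluation should continue for the determination of secondary endpoints". Section 10.6 continues 13-weekly evaluations in subjects without treatment failure and collects survival every 13 weeks. Table 4 footnote 11 starts the progression and survival contact once drug has stopped. The Figure 2 note, itself in Section 10, speaks of withdrawal from further treatment.

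In the SAP, Section 3.3.7 says in its body text that disease assessments are not recorded after treatment discontinuation. The notes to its EFS, Cohort 3 recurrence and PFS censoring tables are narrower: "disease assessments were not recorded after treatment discontinuation due to an AE".

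**The concern.** Leaving treatment and leaving the study are different events, and Section 11.3 attaches different data rules to them. A site that follows the Section 10 sentence would stop collecting data at treatment failure or at any other drug stop. The rest of the protocol requires collection to continue.

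Time to cystectomy, PFS and OS are secondary endpoints in all subjects (Section 9.2). The protocol's introduction says cystectomy is recommended on recurrence after intravesical therapy, so many cystectomies would be expected after treatment failure, exactly when Section 10 would end observation. For EFS, ending observation when drug stops for another reason makes censoring depend on why the drug was stopped. Kaplan-Meier is biased if those subjects have a different risk of failure afterwards.

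**Working it through.** **1. The plan's own figure.** The only stated figure that relies on complete EFS follow-up is the power of at least 80% for 18-month EFS of 20% against 30% (Protocol 17.8, SAP 3.1). Inputs: n = 134, p0 = 0.20, p1 = 0.30, two-sided alpha 0.05 (Protocol 17.1).

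Power = Φ{[(p1 − p0) − 1.96·√(p0(1 − p0)/n)] / √(p1(1 − p1)/n)}
= Φ{[0.10 − 1.96 × 0.03456] / 0.03959} = Φ(0.815) = 79.25%.

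This is within a point of the stated value (137 subjects would give 80%). Other methods give 75.5% (exact binomial, two-sided) and 86.2% (normal, null variance, one-sided 0.05). The point here does not make the stated figure wrong.

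**2. The protocol passages side by side.**

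| Place | What ends at drug stop | What continues |
|---|---|---|
| Section 10 text | participation in the study | nothing stated in that sentence |
| Figure 2 note (Section 10) | treatment | not stated |
| Section 10.6 | treatment | 13-weekly disease evaluation if no failure; survival |
| Section 11.3 | treatment (everything only if consent is withdrawn) | disease evaluation to an event; PFS and OS contact |
| Section 14 | treatment | 13-weekly evaluation for EFS and PFS if no progression, cystectomy or death |
| Table 4 footnote 11 | treatment | progression and survival contact |

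Only the Section 10 sentence ends participation. None of these places expressly lists cystectomy status as an item to collect. Footnote 11 only makes progression contact depend on whether cystectomy has occurred. Otherwise cystectomy rests on the synopsis sentence that further data will be collected as needed for secondary endpoints. It is the least protected endpoint.

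**3. Who is exposed.** Expected EFS events by month 18, before any censoring:
- at 30% EFS: 134 × (1 − 0.30) = 93.8, about 94;
- at the 20% null: 134 × (1 − 0.20) = 107.2, about 107.

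These are ceilings for treatment failures by month 18, because they include deaths as first events. Subjects who stop drug without failure come on top, in a number the documents do not give. The treatment failures have already had their EFS event, so they lose no EFS information. What they can lose is later progression, cystectomy and survival data.

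**4. EFS: illustration only.** Assumptions: exponential EFS with 30% at month 18, visits every 3 months, censoring at the last visit before drug stop, and success when the plain Greenwood 95% interval of the 18-month Kaplan-Meier estimate excludes 20%. The stop rate is the chance of stopping by month 18 if no failure comes first.

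| Stop without failure by month 18 | Simulated power |
|---|---|
| 0% | 75% |
| 10% | 69% |
| 20% | 66% |
| 30% | 61% |
| 40% | 56% |

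If the failure hazard rises 1.5 to 2 times after drug stop, Kaplan-Meier still reads about 30%. True 18-month EFS would then be 28.6–29.2% (10% stopping), 27.4–28.4% (20%) or 26.1–27.7% (30%).

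**The case against.** The strongest reply is that this is one loose phrase which its own cross-reference corrects. It sends the reader to Section 11.3, which separates the two kinds of withdrawal and requires follow-up, and every other passage agrees. Many sites may well have read it that way. That lowers the likelihood of loss but does not remove the contradiction.

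A reader might infer that the Section 10 wording caused the gap the SAP reports. The documents do not show this. The SAP gives no cause, and CRF design is one possible alternative. Taken literally, Section 10 would end follow-up for every discontinuation, whereas the SAP table notes limit the gap to discontinuation due to an AE and concern disease assessments only.

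A reader might also infer that OS and cystectomy data were lost. The SAP points the other way. It censors both at last contact, carries long-term follow-up windows to Month 24 (Sections 3.3.8 and 3.3.9), and plans cystectomy-free days by responder status.

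Finally, some loss does not come from this sentence. Scheduled disease evaluation ends at treatment failure by design (Section 10.6), and the SAP's own rule excludes deaths after discontinuation from EFS and PFS even when they are observed. Rewording Section 10 changes neither. These limits stand.

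**Conclusion.** The contradiction is real and more than clerical. Followed literally, one sentence ends data collection for endpoints defined in all subjects, and the SAP confirms that at least some of the disease assessments required after discontinuation were not recorded. A link between the two is possible but not shown.

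PFS, OS and cystectomy are at risk in all who stop drug. Among them, treatment failures by month 18 number at most about 94 of 134 at 30% EFS and 107 at 20%. It would be wrong to read the 94 as subjects whose outcomes went unobserved, or as a measure of EFS loss. It is a ceiling that assumes sites ignored Sections 10.6, 11.3 and Table 4. EFS is at risk only in those who stop without failure. The power and bias figures for that group rest on assumed stop rates and hazards. For OS and cystectomy the loss is a risk from the wording, not a documented fact. The point merits correction but does not undermine the design.

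**What to change.** 1. Reconcile the Section 10 sentence with Sections 10.6, 11.3, 14 and Table 4. For example: *subjects meeting these criteria are withdrawn from study treatment, and data collection continues per Sections 10.6, 11.3 and 14 and Table 4, except where consent is withdrawn.* The exception is needed because consent withdrawal is on the Section 11.3 list. The criteria for stopping drug are not touched.
2. Name cystectomy status among the items collected at the existing 13-week contact (Table 4 footnote 11, with a matching line in Sections 10.6 and 11.3).
3. For any subject taken off study at drug stop without withdrawing consent, retrieve progression, cystectomy and survival status. If few subjects are still being followed, this matters more than the amendment.
4. In SAP 3.3.7, reconcile the statement that assessments are not recorded after discontinuation with the follow-up required in Protocol 10.6, 11.3 and 14. Say whether the gap covers all discontinuations or only those due to an AE.

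The cost is a one-sentence amendment with a matching line on cystectomy status, a site reminder, an SAP clarification and some data retrieval. No visit is added, and no stated sample size or power figure changes.

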**Figure 1: Disease Evaluation Schedule**

**Figure 2: Study Flow Diagram**

\*Subjects that enter the study with high-grade disease and have documented low-grade disease on study are not considered to have a treatment failure. Subjects who enter with only low-grade T1 disease and who have a recurrence of low-grade T1 disease are considered to have a treatment failure and are withdrawn from further treatment.

## **10.1 Screening Period (Within 8 Weeks ( $\leq$ 56 Days) Before the First Vicinium Treatment)**

Prior to the conduct of any study procedure, signed, written informed consent including HIPAA authorization, if applicable, must be obtained from all potential subjects.

Informed consent must be obtained before a subject undergoes any study-specific tests or procedures, i.e., test or procedures that would not be done as part of routine or standard of care but are being performed only for study purposes (i.e., solely to determine eligibility).

If a patient has had bladder biopsy with or without any other urinary tract biopsy performed (e.g., prostatic urethral biopsy) within the past 8 weeks as part of routine/standard of care, the patient may be asked to sign a pathology evaluation consent form prior to signing the full informed consent form to give permission for their biopsy samples to be sent for central pathology review to determine if the patient would be eligible for the study based on their current disease histology.

Once consent is obtained, subjects will be assigned a subject number ([Section 18.1](#)) and the following assessments and procedures are to be completed within the 8 weeks before the first dose of Vicinium:

- Review of inclusion and exclusion criteria
- Assess and record dates and doses of prior BCG therapy
- Cystoscopy and Biopsies
  - Standard white-light cystoscopy is to be performed. Fluorescence cystoscopy (e.g., blue light cystoscopy) is acceptable but not required. If a subject undergoes fluorescence cystoscopy for biopsy or TURBT during the screening period, this modality should be used for on-study biopsies or TURBTs. However, white-light cystoscopy is appropriate for routine follow-up assessments if a biopsy is not required.
  - Directed biopsies are performed on any area of apparent disease, suspicious disease, or inflammation. If multiple biopsies or TURBTs are required to determine eligibility, the last biopsy or TURBT that confirms eligibility must be within the 8-week screening period. Prior biopsies may be more than 8 weeks before the first dose of Vicinium.
  - For subjects with any papillary disease: All papillary disease must be completely resected e.g., by TURBT, in the screening period.
  - For subjects with T1 disease: the base of the tumor bed must be adequately biopsied so that the sample includes muscle from the base of the lesion(s) in order to demonstrate an absence of muscle invasion. All subjects with T1 disease must undergo a second resection (i.e., restaging TURBT) approximately 2 - 6 weeks after the initial TURBT. Postoperative intravesical chemotherapy (e.g., mitomycin) is acceptable per investigator discretion but cannot be given within 2 weeks of the first dose of Vicinium. For subjects with T1 disease who undergo a restaging TURBT, Vicinium treatment must start within 6 weeks of the restaging TURBT or the last biopsy/TURBT that determines eligibility.
  - **NOTE: Subjects should not receive Vicinium treatment within 2 weeks of any biopsy/TURBT in order to permit bladder healing**

- Additional resections or restaging TURBTs not required by this protocol may also be done at Investigator discretion e.g., for high-grade Ta disease, if this is within acceptable practice standards
- Subjects with T1 disease must also have radiological examination (i.e., CT urogram or MRI urogram) of the abdomen and pelvis to rule out more advanced disease. If intravenous contrast is contraindicated, retrograde ureteropyelography, or CT or MRI without intravenous contrast may be performed.
- Prostatic urethral biopsy (males subjects) is recommended particularly for subjects at higher risk for prostatic urethral involvement per investigator discretion. It is not required.
- Upper tract radiological imaging, i.e., CT urogram or MRI urogram of the abdomen and pelvis, is required if this has not performed within 13 weeks before start of dosing. If intravenous contrast is contraindicated, retrograde ureteropyelography, or CT or MRI without intravenous contrast may be performed. (Note: imaging during screening is a requirement for all subjects with T1 disease as noted above)
- EpCAM determination by immunohistochemistry will be performed on all positive biopsies (baseline and any post-baseline positive biopsies during the study), but confirmation of this is not required prior to enrollment into the trial or the start of study drug administration. Additional unstained slides should be submitted for all positive biopsies for biomarker evaluation ([Section 16.7](#))
- Demographics ([Section 16.1](#))
- Review of medical history, including relevant past medical conditions including other cancers and surgical procedures ([Section 16.1](#))
- Review of medication history (including prescription medications, over-the-counter medications, vitamins, supplements, herbal and homeopathic treatments), including previous anti-tumor treatment(s), and life history of drug allergies and intolerances ([Section 16.1](#))
- 12-lead electrocardiogram(s) (ECGs) for QTc analysis ([Section 16.4](#)). Note: If after the ECG is obtained, the subject begins new medication in the Screening period known to prolong the QT interval, the ECG must be repeated after the new drug reaches steady state and prior to the first dose of study drug.
- Vital signs ([Section 16.5](#))

Not all Screening/Baseline procedures need to be performed on the same day.

